
Methodology:
 
This phase I/II trial is designed as follows:
 
 - Arm A: evaluating the combination of S64315 with azacitidine in the frame of a phase I/II trial and designed in two parts: 
 • A dose escalation phase I part: a Bayesian logistic regression model (BLRM) with escalation with overdose control (EWOC) will be used to guide the dose escalation of the combination. • An expansion phase II part with two sub-arms A1 and A2 previously described. A Bayesian two-stage adaptive design with one interim analysis for futility will be performed in each sub-arm. - Arm B: ██████████ in the frame of a dose escalation phase I part. This arm will also be supported by a BLRM with EWOC. 
Dose escalation methodology and dose-limiting toxicity (DLT) assessment in Arm A
 
The BLRM will be used to estimate the MTD(s) and/or the RP2D based on the occurrence of DLT (defined in section 4.1.3.5), including the S64315 lead-in dose (LID) period and the first cycle of treatment.
 
Toxicities are assessed according to NCI-CTCAE v5.0.
 
The MTD is defined as the highest dosage of S64315 in combination with azacitidine that is unlikely (< 25% posterior probability) to cause DLT in more than 33% of the treated patients up to the end of cycle 1. A maximum of 6 DLT-evaluable patients may be initially enrolled at a dose level, and a minimum of 3 DLT-evaluable patients must be treated at a given dose level before a new higher dose level may be evaluated. More than 6 DLT-evaluable patients may be treated in a cohort at dose levels considered safe according to the BLRM with overdose control in order to better characterize the safety, tolerability, PK, PD, or preliminary clinical activity of S64315 in combination with azacitidine. A minimum of 6 DLT-evaluable patients must have been evaluated at the dose level considered to be the MTD, and before treating patients with this dose in the Phase II part of the study.
 
Only the dose of S64315 will be escalated. The first S64315 weekly full tested dose will be 50 mg; azacitidine will be administered at a fixed dose (75 mg/m²/day for 7 days) in each cycle of treatment. A panel of S64315 doses from 25 mg (dose -1) to 250 mg may be tested according to the dose allocation of the BLRM. Intermediate doses may be proposed depending on available results during the study.
		

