4.1.3.7. Decision process and decision rules

Before testing a new dose level during the dose escalation phase, an EoC meeting between the Sponsor (Therapeutic Area Oncology and Immuno Oncology, Medical Safety Leader, Methodology Department and Clinical Pharmacokinetics department), the coordinator and the investigators will take place to discuss the toxicities in terms of DLTs, safety data, the PK and available PD and the preliminary efficacy data observed in all patients. This meeting will support the decision to escalate to the next dose level of the treatment, to decide jointly of the next dose level to be tested, the go/no go for the expansion phase II part.

If a dose/treatment schedule has not yet been tested, a one-week period should be respected between the C1D2 of the first patient and the C1D2 of subsequent patients of the cohort (between the first and the second infusion in patient of S64315 at the full tested dose). If no medically important or life-threatening toxicity occurs during the one-week observation period, the subsequent patients will be allowed to start treatment without further delays between subsequent patients.

A template of ‘Dose allocation meeting minutes’ is available in [Appendix 6](#).

A Data Safety and Monitoring Board (DSMB) will be set up and will review the safety data before each EoC meeting and provide recommendations to the Sponsor.

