10.2.6. Dose proposed by the model

The dose allocation will start at the dose combination of 50 mg and 75 mg/m² respectively for S64315 and azacitidine.

A maximum of 6 DLT-evaluable patients may be initially enrolled at a dose level, and a minimum of 3 DLT-evaluable patients must be treated at a given dose level before a new higher dose level may be evaluated.

All available data on DLTs, assessed starting from the LID period to C1D28 will be used for updating the model. Before making a dose allocation decision, all patients from a cohort must:

- have been treated with LID1 and LID2, 3 out of 4 S64315 infusions and 5 out of 7 azacitidine injections or
- have had a DLT within the LID period or the first cycle

If a patient is not eligible for inclusion in the Dose-Limiting Toxicity Evaluable Set (DLTES), she/he must be replaced.

If a DLT occurred at LID1, the DLT will be considered as relative to 25 mg of S64315 in monotherapy. If a DLT occurred at LID2, the DLT will be considered as relative to 50 mg of S64315 in monotherapy. In that case, the patient will be replaced to ensure the minimal number of patients needed in the cohort at the full tested dose. Those DLTs will be considered for dose recommendation during the EoC meeting.

At any time during the study, if DLTs occur in the first 2 evaluable patients of a cohort (whether it happened during the LID period or cycle 1), the BLRM could be updated in order to re-evaluate the current dose level before enrolment of any additional patients in the cohort. Once each cohort of patients is completed, the dose recommendation by the model will be based on posterior summaries including the mean, median, standard deviation, 95%-credible interval, and the probability that the true DLT rate for each dose lies in one of the following categories:

- [0,16%) under-dosing
- [16%,33%) targeted toxicity
- [33%,100%] excessive toxicity

Following the principle of EWOC, after each cohort of patients, the dose combinations fulfilling the EWOC criterion (i.e. it is unlikely (<25% posterior probability) that the DLT rate at the dose falls in the excessive toxicity interval) will be identified by the model. A dose not fulfilling the EWOC criterion cannot be recommended.

In addition, admissible dose increments for the next cohort will not exceed 100% of the previous dose of S64315.

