1.1.1.1. Prior specification

The Bayesian approach requires the specification of prior distributions for the two model parameters: α and β .

The same weakly informative prior as the one used in CL1-64315-001 study will be used and also data from CL1-64315-001 study will be used to enrich this same weakly informative prior (see section 1.1.1.2 for details).

The weakly-informative prior bivariate normal prior for the model BLRM parameters ($\log(\alpha)$, $\log(\beta)$) with a reference dose level of 1400mg is obtained as follows:

- The median DLT rate at the S64315 reference dose (1400 mg) was assumed to be 20%, i.e. $\text{mean}(\log(\alpha_1)) = \log(0.25)$
- A doubling in dose was assumed to double odds of DLT, i.e. $\text{mean}(\log(\beta)) = 0$
- The standard deviation of $\log(\alpha)$ was set to 2, and the standard deviation of $\log(\beta)$ to 1, which allows for considerable prior uncertainty for the dose-toxicity profile
- The correlation between $\log(\alpha)$ and $\log(\beta)$ was set to 0

Table (1.1.1.1) 1 summarizes these prior parameters. Table (1.1.1.1) 2 describes the prior obtained for S64315 agent. The effective sample size (ESS) calculated at each dose level is less than 2 patients (weakly-informative prior).

Table (1.1.1.1) 1 - Prior parameters for bivariate normal distribution of model parameters (α_1, β_1)

Parameters	Means	Standard deviations	Correlation
$\log(\alpha_1), \log(\beta_1)$	(-1.386, 0.000)	(2.000, 1.000)	0

Table (1.1.1.1) 2 - Prior distribution summaries derived from priors in Table (8.1.1) 1

S64315 dose (mg)	Prior probabilities that Pr(DLT) is in interval:			Mean	SD	Quantiles			ESS ¹
	[0, 0.16)	[0.16, 0.33)	[0.33, 1]			2.5%	50%	97.5%	
25	0.897	0.049	0.054	0.057	0.140	0.000	0.003	0.548	1.755
50*	0.874	0.059	0.067	0.070	0.155	0.000	0.006	0.610	1.726
100	0.841	0.072	0.086	0.087	0.172	0.000	0.011	0.674	1.700
200	0.795	0.090	0.114	0.111	0.192	0.000	0.022	0.740	1.680
250	0.776	0.098	0.126	0.122	0.200	0.000	0.028	0.761	1.676

*: Starting dose

¹: Effective Sample Size

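### In dose escalation the only model re-check inside a cohort is optional and tied to the first two evaluable patients, so two DLTs elsewhere in a cohort of up to six require no re-check even when the dose then fails the 25% overdose limit

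*Protocol*

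**What the plan says.** **Cohort size.** The synopsis (Methodology), section 4.1.3.3 and section 10.2.6 set a minimum of three evaluable patients before escalating and an initial cap of six: "A maximum of 6 DLT-evaluable patients may be initially enrolled at a dose level". Only going beyond six is conditional on the level being safe according to the model.

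**Routine update.** Section 10.2.6: "Once each cohort of patients is completed, the dose recommendation by the model will be based on posterior summaries".

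**Update inside a cohort.** The same section names one trigger, "if DLTs occur in the first 2 evaluable patients of a cohort", and counts DLTs in cycle 1 and in the lead-in alike. Its consequence is permissive: "the BLRM could be updated in order to re-evaluate the current dose level before enrolment of any additional patients in the cohort". Nothing else in the escalation part prompts a model run before the cohort is complete.

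**Overdose limit.** A dose meets EWOC if "it is unlikely (<25% posterior probability) that the DLT rate at the dose falls in the excessive toxicity interval", that interval being a DLT rate of 33% or more. "A dose not fulfilling the EWOC criterion cannot be recommended". The test is placed after each cohort.

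**Other brakes.** Sections 4.1.3.1 and 4.1.3.7 hold back the second patient at a new dose for one week, after which "the subsequent patients will be allowed to start treatment without further delays between subsequent patients", provided no important toxicity has been seen. Section 4.4.2 pauses the study for a death suspected to be related to S64315. Sections 8.11 and 12.4 allow DSMB recommendations and extraordinary meetings.

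**Expansion part.** Sections 4.1.4 and 10.3.2 make a model update mandatory once the observed DLT rate exceeds 33% after at least four patients, and pause enrolment if EWOC then fails. That trigger does not depend on patient order.

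**The concern.** EWOC exists to limit how many patients are treated at a dose that the data already suggest is too toxic. Here it is applied when a cohort closes. Whether it is looked at sooner depends on which patients had the DLTs, not on what the model would say, and even then the update is permissive. A DLT-free first patient followed by two DLTs leaves up to three further places at that level with no required re-check. Section 4.1.3.6 has every DLT reported to the sponsor within 24 hours, so the information for a prompt re-run would be available.

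The simulations in Appendix 8 do not describe this situation, because they use cohorts of three. Their figures for patients exposed to overtoxic doses do not cover a cohort of six with no intermediate look.

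**Working it through.** **Inputs (Protocol, Appendix 8, sections 1.1.1 to 1.1.3)**
- S64315 power prior for (log α₁, log β₁): means −0.092 and −0.507, SDs 0.982 and 0.694, correlation 0.705, "with a reference dose level of 1400mg".
- Azacitidine: log α₂ with mean −3.75, SD 2; its dose is fixed at its reference, so β₂ drops out.
- Interaction η: mean 0, SD 9.902. Check: (ln 2 / 1.96) × (1400 / 50) = 9.902.
- Co-data weight: 1 / (1 + 2 × 32 × 0.25² / 2²) = 0.50.

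**Model (section 10.2.2).** logit π₁ = log α₁ + β₁ log(d/1400); logit π₂ = log α₂; combination odds = exp(η d/1400) × (π₁ + π₂ − π₁π₂) / [(1 − π₁)(1 − π₂)]. Posteriors come from weighting 2,000,000 prior draws by the binomial likelihood.

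**Step 1: reproduce the printed figures.** P(over) is the probability of a DLT rate of 33% or more.

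| Quantity | Printed | Recomputed |
|---|---|---|
| Prior P(over), 50 mg | 0.143 | 0.144 |
| Prior P(over), 100 mg | 0.241 | 0.240 |
| After 0/5 at 50 mg: P(over), 100 mg | 0.0666 | 0.067 |
| After 1/5 at 50 mg: P(over), 100 mg | 0.2246 | 0.222 |
| After 2/5 at 50 mg: P(over), 25 mg | 0.2032 | 0.194 |
| After 2/5 at 50 mg: P(target), 25 mg | 0.4456 | 0.449 |
| After 3/5 at 50 mg | no safe dose | lowest dose 0.45, none safe |

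The printed Table (1.3) 1 already shows the point. After 2/5 it moves to 25 mg. Recomputed P(target) is higher at 50 mg (0.48) than at 25 mg (0.45), so under the simulation allocation rule (highest P(target) among doses meeting EWOC) the move is explained by 50 mg failing EWOC. A sixth patient at 50 mg is nevertheless permitted.

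**Step 2: P(over) at 50 mg inside the first cohort, limit 0.25**

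| DLTs / evaluable | Printed normal prior | Un-approximated power prior |
|---|---|---|
| 2/3 | 0.49 | 0.46 |
| 2/4 | 0.38 | 0.35 |
| 2/5 | 0.29 | 0.26 |
| 2/6 | 0.22 | 0.20 |
| 3/5 | 0.58 | 0.56 |

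Two DLTs among three to five patients fail; 2/5 is the closest to the limit. A single early DLT (1/2) sits on the limit (0.26 or 0.24 by the same two priors) and is not counted below, which starts at the second DLT.

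**Step 3: how often it arises.** Cohort of six, true DLT rate p, each outcome known before the next patient starts.
- Strict reading (trigger = DLTs in both of patients 1 and 2): P(at least 2 DLTs in the first 5) − p². At p = 0.22: 1 − 0.78⁵ − 5 × 0.22 × 0.78⁴ = 0.304; 0.304 − 0.048 = 0.256.
- Broad reading (any DLT in patients 1 and 2 fires it): (1 − p)² × [3p²(1 − p) + p³]. At p = 0.22: 0.608 × 0.124 = 0.075.

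| True rate | Source | Trigger fires (strict) | Further enrolment after failure, trigger unmet (strict) | Same (broad) |
|---|---|---|---|---|
| 22% | scenario b, 50 mg | 5% | 26% | 8% |
| 27% | scenario c, 50 mg | 7% | 34% | 10% |
| 33% | edge of excessive interval | 11% | 42% | 11% |
| 45% | scenario d, 50 mg | 20% | 54% | 13% |

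In the strict-reading cohorts affected, 1.9 to 2.2 further patients are enrolled on average.

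**The case against.** **The trigger wording is open.** A DLT-free patient becomes evaluable only at the end of cycle 1, whereas a patient with a DLT counts at once. Patients 2 and 3 could thus be the first two evaluable patients. This stands: the strict percentages are one reading, and the wording itself needs settling.

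**Accrual overlaps.** The DLT window is about six weeks and the only stagger is one week, once. Suppose evaluability is ordered by time, DLT times are uniform over six weeks and arrivals are exponential (assumptions, not in the documents). Then late enrolment with the trigger unmet, at a true rate of 45%, is about 4% of cohorts at one patient a week, 19% at one per two weeks and 35% at one per four weeks, against 54%. This also stands.

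**Other controls exist.** Six is a maximum and a cohort may close at three; the sponsor coordinates assignment and is notified of each DLT; the DSMB can act. These are real but discretionary, and none is a model re-check.

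**A reader might infer that the protocol breaks its own EWOC rule.** The documents do not support that. Section 10.2.6 applies EWOC after each cohort, to the dose recommended next, and does not extend it to patients still entering an open cohort. Nor should 54% be taken as the expected frequency: it belongs to a scenario that Appendix 8 calls unlikely, while scenarios b and c are called the most likely.

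**Conclusion.** The point holds as a gap in the escalation design. The within-cohort update is optional and depends on patient order, so it can go unused when the protocol's own model would put the current dose above the 25% limit. The failing pairs at 50 mg (2/3, 2/4, 2/5) hold under both forms of the prior, with 2/5 borderline.

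The frequency is uncertain. Under sequential outcomes it is about 26% to 54% of six-patient cohorts on the strict reading and 8% to 13% on the broad one, for true rates of 22% to 45%; overlapping accrual lowers it further. No stated rule is breached, and the change is an inexpensive safety improvement. The SAP (sections 1.3 and 1.3.1) reports that escalation was stopped and expansion will not be conducted, so the point concerns the design as written and any reuse of it.

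**What to change.** Reconcile the cap, the trigger and the EWOC limit in section 10.2.6, section 4.1.3.3 and the synopsis:
- Change the update from permissive to mandatory and make it independent of patient order, as the expansion rule already is: the BLRM will be updated whenever a second or later DLT occurs in a cohort.
- Have the sponsor and investigators, with the DSMB as needed, review the result before any additional patient is enrolled at that level. Leave the enrolment decision to that review and do not close the level automatically.
- Tabulate in Appendix 8 the DLT/patient pairs that fail EWOC at each level.

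**Cost.** A few extra model runs, a pause for review, and some reviews at doses that later prove acceptable. A second DLT with EWOC failing occurs by patient five in 30% (true rate 22%) to 41% (true rate 27%) of six-patient cohorts. Run on to six, 59% and 51% of those would end at 2/6, which passes: 10 × 0.22² × 0.78⁴ / 0.304 = 0.59 and 10 × 0.27² × 0.73⁴ / 0.409 = 0.51. That is the reason to require a review and not an automatic halt.

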Appendix 6: Dose allocation meeting minutes template.....	153
Appendix 7: Guidance for diarrhoea management (ESMO, 2018).....	154
Appendix 8: Statistical aspects for the dose escalation phase I part and the expansion phase II part with an interim analysis for futility	155
Appendix 9: Local modification of the clinical study protocol	171
Appendix 10: Instructions to investigator for handling data rights requests.....	172

List of abbreviations

%	: percent
μmol	: micromole
ADL	: Activities of Daily Living
ADME	: Absorption Distribution Metabolism Excretion
AE	: Adverse Event
ALP	: ALkaline Phosphatase
ALT	: ALanine aminoTransferase
AML	: Acute Myeloid Leukaemia
ANC	: Absolute Neutrophil Count
APL	: Acute Promyelocytic Leukaemia
aPTT	: activated Partial Thromboplastin Time
AST	: ASpartate aminoTransferase
AUC	: Area Under the Curve
AUC24	: Area Under the Curve at 24 hours
AUClast	: Area under the concentration-time curve from time zero to time of last measurable concentration
AUC _τ	: Area under the plasma concentration-time curve
AVB	: AtrioVentricular Block
AZA	: Azacitidine
β hCG	: β Human Chorionic Gonadotrophin
BCL2	: B-cell lymphoma 2 gene
Bcl-2	: B-cell lymphoma 2 protein
BH3	: Bcl-2 Homology domain 3
BLRM	: Bayesian Logistic Regression Model
BMA	: Bone Marrow Aspirate
BMB	: Bone Marrow Biopsy
BMMC	: Bone Marrow-derived Mononuclear Cells
BMI	: Body Mass Index
BNP	: Brain Natriuretic Peptide
BP	: Blood Pressure
BR	: Best Response
bpm	: beats per minute (heart rate unit)
BSA	: Body Surface Area
BNP	: Brain Natriuretic Peptide
BUN	: Blood Urea Nitrogen
C	: Cycle
CABG	: Coronary Artery Bypass Graft
CAD	: Coronary Artery Disease
CI	: Confidence Interval
C _{inf}	: Concentration at the end of infusion
CISO	: Chief information security officer
CK	: Creatine Kinase
CL	: total CLearance
C _{last}	: Last quantifiable observed concentration
CLL	: Chronic Lymphocytic Leukaemia
cm	: Centimetre
C _{max}	: maximum Concentration

C _{min}	: minimum Concentration
CMP	: Clinical Monitoring Plan
CNS	: Central Nervous System
CPK	: Creatine Phosphokinase
CPK-MB	: Creatine PhosphoKinase Myocardial Band
CR	: Complete Remission
CRA	: Clinical Research Associate
CRi	: Complete Remission with incomplete haematologic recovery
CR _{MRD}	: Complete Remission without Minimal Residual Disease
CRO	: Contract Research Organisation
CSR	: Clinical Study Report
CTCAE	: Common Terminology Criteria for Adverse Events
CT	: Computed Tomography
CV	: Curriculum Vitae
CXR	: Chest X-Ray
D	: Day
DBP	: Diastolic Blood Pressure
DDI	: Drug-Drug Interaction
DFS	: Disease-Free Survival
DLT	: Dose Limiting Toxicity
DLTES	: Dose-Limiting Toxicity Evaluable Set
DSMB	: Data Safety and Monitoring Board
DOR	: Duration Of Response
DPO	: Data Protection Officer
e.g.	: Exempli gratia (for example)
ECG	: ElectroCardioGram
ECHO	: Echocardiogram
EAE	: Emergent Adverse Event
eCRF	: Electronic Case Report Form
ECOG	: Eastern Cooperative Oncology Group
EMA	: European Medicines Agency
EoC	: End of Cohort
EoI	: End of Infusion
ERIN	: Event Requiring Immediate Notification
EWOC	: Escalation With Overdose Control
FAS	: Full Analysis Set
FDA	: Food and Drug Administration
FFPE	: Formalin-Fixed Paraffin-Embedded
FU	: Follow-Up
FVFP	: First Visit First Patient
g	: Gram
G/L	: Giga (10 ⁹) per litre
GCP	: Good Clinical Practice
GGT	: Gamma-Glutamyl Transferase (Gamma-Glutamyl Transpeptidase)
GI	: GastroIntestinal
GLP	: Good Laboratory Practice
GLS	: Global Longitudinal Strain
GMP	: Good Manufacturing Practice
GVHD	: Graft-versus-host disease

h	: Hour
HBs	: Surface antigen of Hepatitis B virus
hERG	: Ether-à-go-go-Related Gene
HIV	: Human Immunodeficiency Virus
HMA	: HypoMethylating Agents
HNSTD	: Highest Non Severely Toxic Dose
HPLC	: High-Performance Liquid Chromatography
HR	: Heart Rate
HSCT	: Haematopoietic Stem Cell Transplant
IB	: Investigator's Brochure
ICF	: Informed Consent Form
ICH	: International Conference on Harmonisation
ICTR	: International Centre for Therapeutic Research
i.e.	: id est (that is)
IEC	: Independent Ethics Committee
IMP	: Investigational Medicinal Product: a pharmaceutical form of an active ingredient or placebo being tested or used as a reference in a clinical trial i.e. S64315 and azacitidine
INR	: International Normalized Ratio
IRB	: Institutional Review Board
I.R.I.S.	: Institut de Recherches Internationales Servier
IRR	: Infusion Related Reaction
IS	: Included Set
IU	: International Unit
IUD	: IntraUterine (contraceptive) Device
IUS	: IntraUterine hormone-releasing System
IV	: IntraVenous (route)
kg	: Kilogram
L	: Litre
LDH	: Lactate DeHydrogenase
LDL	: Low-Density Lipoprotein
LFT	: Liver Function Tests
LID	: Lead-In Dose
LLN	: Lower Limit of reference range
LV	: Liposomal Vehicle
LVEF	: Left Ventricular Ejection Fraction
MCL1	: HGNC Approved Gene Symbol for Myeloid Cell Leukaemia Sequence 1
Mcl-1	: Induced myeloid leukaemia cell differentiation protein
MDRD	: Modification of Diet in Renal Disease
MDS	: MyeloDysplastic Syndrome
MedDRA	: Medical Dictionary for Regulatory Activities
mg	: Milligram
MI	: Myocardial Infarction
min	: Minute
mL	: Millilitre
mm	: Millimetre
mmHg	: Millimetre of mercury
mmol	: Millimole
msec	: Millisecond

MLFS	: Morphologic Leukaemia-Free State
MM	: Multiple Myeloma
MRD	: Minimal (measurable) Residual Disease
MS/MS	: tandem Mass Spectrometry
MTD	: Maximum Tolerated Dose
MUGA scan	: Multi-Gated Acquisition scan
NA	: Not Applicable
NAE	: Number of Adverse Events
NCA	: Non-Compartmental Analysis
NCI	: National Cancer Institute
NCT	: EudraCT Number
NGS	: Next Generation Sequencing
ng	: Nanogram
NTI	: Narrow Therapeutic Index
NS	: Not statistically Significant
NYHA	: New York Heart Association
OPM	: OPERating Manual
ORR	: Overall Response Rate
OS	: Overall Survival
p.o.	: per os (orally)
PBMC	: Peripheral Blood-derived Mononuclear Cells
PBPK	: Physiologically-based Pharmacokinetic
PD	: Pharmacodynamics
PDX	: Patient-Derived Xenograft
PFS	: Progression Free Survival
PG	: Pharmacogenomics
P-GP	: P-glycoprotein 1
Ph. Eur.	: European Pharmacopeia
PK	: Pharmacokinetics
PR	: Partial response
po	: per os (orally)
PPS	: Per Protocol Set
PS	: Performance Status
QC	: Quality Control
QD	: Once daily
QTc	: QT interval corrected for heart rate
QTcF	: QTc interval corrected with Fridericia's formula
RBC	: Red Blood Cells
RNA	: Ribonucleic acid
RP2D	: Recommended Phase II Dose
SAE	: Serious Adverse Event
SBP	: Systolic Blood Pressure
SC	: SubCutaneous (route)
SD	: Standard Deviation
SLL	: Small Lymphocytic Lymphoma
SE	: Standard Error
sec	: Second
SmPC	: Summary of Product Characteristics
SoI	: Start of Infusion
SS	: Safety Set

SUSAR	: Suspected Unexpected Serious Adverse Reaction
T	: Temperature
$t_{1/2}$: terminal half-life
TdP	: Torsades de Pointes
test drug	: Drug substance in a given dosage form, tested in a clinical trial, i.e. S64315
t_{last}	: Time corresponding to C_{last}
TLS	: Tumour Lysis Syndrome
t_{max}	: Time corresponding to C_{max}
TPN	: Total parenteral nutrition
TSH	: Thyroid Stimulating Hormone
TTE	: TransThoracic Echocardiography
TU	: Therapeutic Unit
ULN	: Upper Limit of reference range
USP-NF	: United States Pharmacopeia and The National Formulary
Vd	: Volume of distribution
WBC	: White Blood Cells
WHO	: World Health Organization
WHO-DD	: World Health Organization, Drug Dictionary
WMA	: World Medical Association
WOCBP	: Woman of Child Bearing Potential
WV	: Withdrawal Visit

